12.3. Reporting Adverse Events

12.3.1. Adverse Event Reporting

An AE is defined as any untoward medical occurrence in a subject administered a pharmaceutical product and which does not necessarily have to have a causal relationship with this treatment. AEs may be reported by the subject, discovered by the Investigator and Investigator’s staff, or detected through physical examination, laboratory test, or other means.

AEs include:

- Any unfavorable and unintended sign, medical diagnosis, or symptom that occurs between the time the first administration of study drug and the study duration required by the protocol

- Any new undesirable medical experience or an unfavorable and unintended change of an existing condition that occurs between the time the first administration of study drug and the study duration required by the protocol, whether or not considered related to study drug
- Abnormal laboratory findings considered by the Investigator to be clinically significant, i.e., those that are unusual for the population being studied or individual subject

Whenever possible, the Investigator should group signs or symptoms that constitute a single diagnosis into a single event term. For example, cough, rhinitis, and sneezing might be grouped together as *upper respiratory tract infection*.

In cases where the Investigator notices an unanticipated benefit to the subject, study site personnel should enter *unanticipated benefit* with the actual event term (for example, the complete actual term would be *unanticipated benefit-sleeping longer*).

AEs will be collected from the time informed consent is obtained until the last Follow-Up visit. All AEs will be documented in the source records and will be recorded in the CRFs as appropriate. All AEs, whether observed by the Investigator or reported by the subject, and whether or not thought to be related to the study drug, will be recorded on the appropriate CRF. In describing AEs on the CRF, standard, medically accepted terminology will be used.

The description of each AE will identify the date of onset, duration, severity (see Section 12.2.2 for Definitions of Severity), any action taken (including any diagnostic procedures or laboratory tests performed and all treatments which were administered), the outcome of the event, and relationship to the study drug.

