4. STUDY DESIGN

This is a Phase 2, multicenter study of OMS721 in subjects with the following diseases: IgAN, lupus nephritis, MN, or C3 glomerulopathy including dense deposit disease. Three cohorts will be enrolled:

- Cohort 1 will be subjects with corticosteroid-dependent IgAN, LN, MN, or C3 glomerulopathy. All Cohort 1 subjects will be receiving a corticosteroid dose of > 10 mg of prednisone or equivalent dose for at least 12 weeks. Cohort 1 subjects will all receive OMS721 4 mg/kg intravenously (IV) once weekly for 12 weeks.
- Cohort 2 will be subjects with IgA nephropathy who are not receiving corticosteroids. Cohort 2 subjects will receive either OMS721 4 mg/kg IV treatment or 5% dextrose in water (D5W) vehicle once weekly for 12 weeks in a randomized double blind design.
- Cohort 3 will be subjects with IgA nephropathy who are not receiving corticosteroids. Subjects in Cohort 3 will receive either OMS721 370 mg IV or 5% dextrose in water (D5W) vehicle in a randomized double blind design. Regardless of treatment assignment, subjects in Cohort 3 will be eligible for additional open-label OMS721 treatment if they fail to achieve a 24-hour urine protein < 50% of baseline or their 24-hr urine protein is > 1000mg/24-hours after 12 weeks of dosing [plus a 6-week follow-up period].

Cohorts 1 and 2 are ongoing at the time of Protocol Amendment 02. Upon approval of this amendment, subjects with IgAN in Cohort 1 and subjects in Cohort 2 who have started study drug and are on study will be offered the opportunity to roll into Cohort 3 for extended treatment and long-term follow-up. Subjects have to sign an informed consent and meet the eligibility criteria in order to participate in Cohort 3. The rollover subjects will not be randomized and will receive open-label OMS721 370 mg IV once per week for the remaining treatment period of their original cohort. Following rollover they will follow all study procedures for Cohort 3. Subjects with IgAN in Cohort 1 must have discontinued corticosteroids in order to roll into Cohort 3. Subjects with LN, MN or C3 glomerulopathy in Cohort 1 are not eligible rollover to Cohort 3.

Approximately 44 subjects will be enrolled (16 in Cohort 1, 10 in Cohort 2, and 18 in Cohort 3) from up to approximately 15 investigative sites.

For all subjects in Cohort 1 and Cohort 2, the study will consist of screening (4 weeks), treatment (12 weeks), and follow-up (6 weeks) periods.

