12. EFFICACY ANALYSIS

12.1. General Considerations

All data summaries will be descriptive in nature and efficacy summaries will be presented by disease group, cohort and treatment. Summary statistics for continuous variables will include number of subjects, mean, median, standard deviation, minimum, and maximum. For categorical variables, frequencies and percentages will be provided. Baseline value will be calculated according to Section 8.3.1. All confidence intervals will be constructed at the two-sided 95% confidence level.

The data collected during the re-treatment period for the rollover subjects in Cohort 1 and Cohort 2 will be presented in listings. Because the open-label OMS721 dose is different from the original OMS721 dose and re-treatment is optional, statistical analyses for Cohort 1 and Cohort 2 will include the data collected in the initial treatment period and the initial follow-up period only. Statistical analyses for Cohort 3 will include the subjects who are randomized in Cohort 3 only. All data collected for the randomized subjects in Cohort 3 will be summarized.

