13. SAFETY AND TOLERABILITY

13.1. Overall Summary of Safety

An overall summary of treatment-emergent adverse events, which is defined as the AEs occurring or worsening after the start of study treatment, will be provided by disease group, cohort and treatment. All AEs will be coded by MedDRA. The following items will be included in the overall summary:

- Subject incidence of treatment-emergent AEs
- Subject incidence of treatment-related AEs (defined as probable or possible related to study drug)
- Subject incidence of treatment-emergent AEs by maximum CTCAE grade
- Subject incidence of treatment-emergent serious AEs (SAEs)
- Subject incidence of treatment-emergent AEs leading to discontinuation of study drug
- Subject incidence of treatment-emergent AEs leading to discontinuation of study
- Subject incidence of treatment-emergent fatal AEs
- Total number of unique treatment-emergent AE MedDRA preferred terms
- Median number of unique treatment-emergent AE MedDRA preferred terms per subject
- Total number of unique treatment-emergent SAE MedDRA preferred terms
- Median number of unique treatment-emergent SAE MedDRA preferred terms per subject

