13.2. Adverse Event Preferred Term and Body/Organ System Summary Tables

Subject incidence of the following AEs will be provided by disease group, cohort and treatment:

- pre-treatment AEs by MedDRA SOC and preferred term (pre-treatment AEs are those AEs that occurred prior to the start of study treatment)

- treatment-emergent AEs by MedDRA SOC, and preferred term
- treatment-emergent AEs by MedDRA preferred term
- treatment-related AEs by MedDRA SOC, and preferred term
- treatment-emergent AEs by MedDRA preferred term, and maximum CTCAE grade
- AEs leading to study drug discontinuation by MedDRA SOC, and preferred term
- AEs leading to study discontinuation by MedDRA SOC, and preferred term
- treatment-emergent SAEs by MedDRA SOC, and preferred term
- treatment-related SAEs by MedDRA SOC, and preferred term
- AEs leading to death by MedDRA SOC, and preferred term

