13.3. Study Treatment Adherence and Extent of Exposure

Because all dosing will be under direct supervision of study personnel, treatment adherence will not be analyzed. Dosing information will be listed.

The total dose volume (mL) received, the total intended dose volume (mL) and the number of doses received will be summarized for scheduled visits and unscheduled visits by disease group, cohort and treatment. Intended dose volume at each dose administration for Cohort 1 and Cohort 2 is calculated as

$$4 \text{ mg/kg} \times \text{Weight (kg)} \div \text{Drug concentration.}$$

If the weight is greater than 100 kg, the intended dose volume will be calculated using 100 kg. This study uses two drug concentrations, 100 mg/mL and 185 mg/mL.

In addition, relative dose intensity (%), defined as the total dose volume received as a percentage of the total intended dose volume will be summarized for scheduled visits and unscheduled visits by disease group. Listing of dosing information will also be provided.

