13.5. Routine Laboratory Data

Summary statistics for actual values and for change from baseline will be tabulated as appropriate for laboratory results by scheduled visit, disease group, cohort and treatment. Subjects with laboratory values outside of the normal reference range at any post-baseline safety assessment will be listed by disease group, cohort and treatment.

Shifts from baseline laboratory values (normal/abnormal) will be tabulated by disease group, cohort and treatment.

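### SAP section 13 does not cut safety summaries at the first open-label dose, so events and exposure on OMS721 can be reported under vehicle in Cohort 3

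*SAP*

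**What the plan says.** SAP 13.1 gives an overall summary of treatment-emergent AEs (TEAEs), "which is defined as the AEs occurring or worsening after the start of study treatment, will be provided by disease group, cohort and treatment". The definition has a start and no stop. SAP 13.2 uses the same grouping for the preferred-term and organ-class tables: "Subject incidence of the following AEs will be provided by disease group, cohort and treatment". For exposure, SAP 13.3 says that "the number of doses received will be summarized for scheduled visits and unscheduled visits by disease group, cohort and treatment", and SAP 13.5 has summary statistics "tabulated as appropriate for laboratory results by scheduled visit, disease group, cohort and treatment". SAP 8.3.2 defines the safety population by receipt of any study drug and adds no as-treated or period rule.

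Other sections decide what falls into those columns:

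- Protocol 12.3.1: "AEs will be collected from the time informed consent is obtained until the last Follow-Up visit". In Cohort 3 that visit is at week 104, Day 722.
- SAP 4 on Cohort 3: "Regardless of treatment assignment, subjects in Cohort 3 will be eligible for additional open-label OMS721 treatment", subject to the proteinuria criteria after the 6-week follow-up. Courses can repeat during weeks 18 to 91.
- SAP 4 on rollover from Cohorts 1 and 2: these subjects "will receive open-label OMS721 370 mg IV once per week for the remaining treatment period of their original cohort".
- SAP 12.1, under efficacy, limits Cohorts 1 and 2 to the initial treatment and initial follow-up periods. For Cohort 3 it says: "All data collected for the randomized subjects in Cohort 3 will be summarized".
- Protocol 13.2.1 treats rollover subjects as a separate cohort and asks for safety to be summarised overall as well. SAP section 13 repeats neither instruction.

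**The concern.** Movement from vehicle to OMS721 is built into Cohort 3. Entry requires more than 1000 mg of urine protein per 24 hours (protocol 8.1). A vehicle subject whose proteinuria has not changed by week 18 is therefore above 1000 mg and at 100% of baseline, and meets both re-treatment criteria. Protocol 7.2 explains that the cohort was added so that such subjects could have active drug.

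If the treatment label stays with the randomised arm for the whole study, an event that OMS721 causes in such a subject is shown under vehicle. The usual effect is to make the drug look closer to vehicle than it is. In this trial the descriptive columns are the whole of the primary analysis, so the definition of a column matters more than it would beside a formal comparison.

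**Working it through.** **Inputs.** Planned cohort sizes are 16, 10 and 18 (SAP 4), and 16 + 10 + 18 = 44, as stated. Allocation in Cohorts 2 and 3 is 1:1 (protocol 9.1.2). Assuming exact halves, there are 5 vehicle subjects in Cohort 2 and 9 in Cohort 3. The schedule follows day = (week − 1) × 7 + 1, which returns the plan's own Day 120 for week 18 and Day 722 for week 104.

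**Weight of one subject.** In Cohort 3, 1/9 = 11.1 percentage points. In Cohort 2 at its planned size, 1/5 = 20 points.

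**Open time.** (722 − 120)/722 = 602/722 = 83% of post-dose AE collection in Cohort 3 falls after Follow-Up Visit 2. This is calendar time. One 12-week course is 84 days, and 84/722 = 12%.

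**Exposure.** SAP 8.1 defines duration as last dose + 7 − first dose. For the blinded course, 78 + 7 − 1 = 84 days. If one re-treatment course starts on Day 120, its twelfth dose is on Day 120 + 77 = 197, and duration becomes 197 + 7 − 1 = 203 days: 84 on vehicle, a gap of 35, and 84 on OMS721. So 84/203 = 41% of the duration in the vehicle column, and 12 of its 24 doses, would be OMS721.

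**Labs, if re-treatment visits are mapped by study day.** Study day = RT1 day + RT day − 1. With RT1 on Day 120, RT9 (RT day 57) falls on 120 + 57 − 1 = 176, the exact target for Follow-up Visit 3 (SAP Table 2, window 149 to 221). Re-treatment labs are drawn at RT1, RT2, RT5, RT9 and RTFU. Under Table 2's nearest-to-target rule, with ties going to the later value:

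- RT1 on Days 120 to 134 selects RT9, drawn after 8 OMS721 doses. On Day 134, RT5 falls on Day 162 and RT9 on Day 190, both 14 days from target.
- RT1 on Days 135 to 148 selects RT5, drawn after 4 doses.

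This assumes visits on schedule and no regular Follow-up Visit 3 during the course, in line with protocol 10.1.11.

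**Illustration.** The documents give no event rates or uptake, so these are assumptions: risk p0 = 5% on vehicle, p1 = 25% per OMS721 course, share f of vehicle and share g of OMS721 subjects taking one open-label course. Vehicle column = 1 − (1 − p0)(1 − f·p1). OMS721 column = 1 − (1 − p1)(1 − g·p1).

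| f, g | OMS721 | Vehicle | Difference (points) | Ratio |
|---|---|---|---|---|
| blinded course only | 25.0% | 5.0% | 20.0 | 5.0 |
| 0.5, 0.5 | 34.4% | 16.9% | 17.5 | 2.0 |
| 1, 1 | 43.8% | 28.8% | 15.0 | 1.5 |
| 1, 0.5 | 34.4% | 28.8% | 5.6 | 1.2 |
| 1, 0 | 25.0% | 28.8% | −3.8 | 0.9 |

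With open-label risk q and 9 vehicle subjects, the chance that at least one on-drug event is counted under vehicle is 1 − (1 − q·f)^9. This gives 10.7% at q = 5%, f = 25%; 37.0% at q = 10%, f = 50%; and 86.6% at q = 20%, f = 100%.

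**The case against.** The study is descriptive and unpowered, and vehicle differences with confidence intervals are specified only for efficacy (SAP 12.6 to 12.8). Onset dates and causality are recorded and dosing is listed, so attribution for about 9 subjects could be rebuilt by hand. SAP 18 places the two Cohort 3 interim analyses around the end of the blinded period. The shells are a separate document (SAP 20.1) and may already split the periods. These points lower the severity but do not supply the rule. The SAP 18 looks wait for a whole group to finish and have no per-subject cut, so subjects enrolled early may already have open-label data.

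Several stronger readings are tempting, and the documents do not support them.

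- **That the SAP requires on-drug events to go under vehicle.** It does not say which meaning of treatment applies. The protocol's TEAE definition (13.2.10.2) also has no stop, so this is an omission that both documents share.
- **That all Cohort 2 vehicle subjects are affected.** Protocol 13.2.1 puts rollovers in their own cohort, and SAP 12.1, if read across to safety, removes data after the initial follow-up. What remains is a vehicle subject who rolls over during the initial 12 weeks and is kept in the Cohort 2 column. The number is unknown, and undosed Cohort 2 screenees move to Cohort 3 (protocol 10.1.1).
- **That re-treatment labs certainly enter the follow-up windows.** SAP 5.2 gives RT visits their own names and day count, and Table 2 does not list them. Day-based mapping is one reading.
- **That 83% of follow-up is spent on OMS721, or that the comparison would reverse.** The first confuses calendar time with drug time. The second needs far higher uptake in the vehicle arm than in the OMS721 arm, plus assumed rates.

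**Conclusion.** The gap is real for Cohort 3. No section of either document says how an AE or a dose during open-label re-treatment is assigned in the randomised columns. The open-ended TEAE definition, together with the all-data rule in SAP 12.1 if that is carried over to safety, allows it to be shown under vehicle. Each affected subject moves the Cohort 3 vehicle column by about 11 points, assuming 9 vehicle subjects. With equal uptake in both arms, the illustrated difference narrows from 20.0 to between 17.5 and 15.0 points. Larger shifts depend on unequal uptake. The Cohort 2 and laboratory consequences are conditional, as set out above. The SAP should be changed on this point, but the omission does not undermine the trial.

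A reader might also infer that leaving out the protocol's overall safety summary is a breach. That goes too far: protocol 13.2 allows method changes to be described in the study report, subject counts can be added across cells, and the shells may hold a total column. It is a minor presentation point.

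**What to change.** In SAP section 13:

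1. In the randomised OMS721 and vehicle columns, count AEs, exposure and safety labs from the first dose to the earlier of Follow-Up Visit 2 (Day 120) and the first open-label 370 mg dose.
2. Show rollover, re-treatment and later off-drug follow-up events separately, each with subject-weeks. State that rollover subjects form their own group from their first open-label dose. Their earlier data then stay in Cohorts 1 and 2, consistent with SAP 12.1. This makes the timing explicit where protocol 13.2.1 is silent.
3. Add one descriptive column for any OMS721 exposure, counting from each subject's first OMS721 dose, so that no on-drug event is lost. It would hold between 16 + 5 + 9 = 30 subjects and, if every vehicle subject crossed over, 44.
4. In SAP 8.2.3, label RT1 to RTFU by course and keep them out of the Table 2 follow-up windows.
5. Carry the protocol's overall safety summary into the shells.

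If the shells already do this, a short statement in section 13 is enough.

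The cost is SAP wording, visit labels and a few extra columns, with no new data. Rollover subjects will have less time at risk in the randomised columns, which is why subject-weeks are needed. The any-exposure column mixes diseases, the 4 mg/kg and 370 mg doses and steroid use, so it supplements the by-cohort columns and does not replace them.

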13.2. Adverse Event Preferred Term and Body/Organ System Summary Tables

Subject incidence of the following AEs will be provided by disease group, cohort and treatment:

- pre-treatment AEs by MedDRA SOC and preferred term (pre-treatment AEs are those AEs that occurred prior to the start of study treatment)

- treatment-emergent AEs by MedDRA SOC, and preferred term
- treatment-emergent AEs by MedDRA preferred term
- treatment-related AEs by MedDRA SOC, and preferred term
- treatment-emergent AEs by MedDRA preferred term, and maximum CTCAE grade
- AEs leading to study drug discontinuation by MedDRA SOC, and preferred term
- AEs leading to study discontinuation by MedDRA SOC, and preferred term
- treatment-emergent SAEs by MedDRA SOC, and preferred term
- treatment-related SAEs by MedDRA SOC, and preferred term
- AEs leading to death by MedDRA SOC, and preferred term

13.3. Study Treatment Adherence and Extent of Exposure

Because all dosing will be under direct supervision of study personnel, treatment adherence will not be analyzed. Dosing information will be listed.

The total dose volume (mL) received, the total intended dose volume (mL) and the number of doses received will be summarized for scheduled visits and unscheduled visits by disease group, cohort and treatment. Intended dose volume at each dose administration for Cohort 1 and Cohort 2 is calculated as

$$4 \text{ mg/kg} \times \text{Weight (kg)} \div \text{Drug concentration.}$$

If the weight is greater than 100 kg, the intended dose volume will be calculated using 100 kg. This study uses two drug concentrations, 100 mg/mL and 185 mg/mL.

In addition, relative dose intensity (%), defined as the total dose volume received as a percentage of the total intended dose volume will be summarized for scheduled visits and unscheduled visits by disease group. Listing of dosing information will also be provided.

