9.2. Study Drug Accountability

For Cohorts 2 and 3, the investigator will designate an unblinded pharmacist and/or designee who will be responsible for study drug accountability.

In compliance with U.S. Food and Drug Administration (FDA), European Medicines Agency (EMA), and other applicable regulations, records will be maintained by the investigator and/or pharmacist designee for OMS721 study drug product delivery to the site, the inventory at the site, the use of each vial, and the return of used and unused drug product, including dates and quantities. The investigator and/or pharmacist designee will maintain the investigative site's study drug accountability documentation. The documentation should include which drug product was used [REDACTED]. After the study has been completed, a copy of the investigator/pharmacy drug accountability records will be provided to the Sponsor. The original drug accountability records will be retained by the site.

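### SAP 13.3 totals exposure in mL rather than mg although two drug concentrations are used, and gives no intended-volume formula for the fixed-dose Cohort 3

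*SAP*

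**What the plan says.** SAP section 13.3 plans the exposure summary by disease group, cohort and treatment: "The total dose volume (mL) received, the total intended dose volume (mL) and the number of doses received will be summarized". It then adds: "This study uses two drug concentrations, 100 mg/mL and 185 mg/mL".

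The intended volume has a stated scope: "Intended dose volume at each dose administration for Cohort 1 and Cohort 2 is calculated as" 4 mg/kg times weight, divided by drug concentration. There is a cap: "If the weight is greater than 100 kg, the intended dose volume will be calculated using 100 kg". Dose intensity is a percentage built on the same quantities: "relative dose intensity (%), defined as the total dose volume received as a percentage of the total intended dose volume". It is summarised by disease group. Dosing information is also listed.

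The regimens are in SAP section 4. For Cohort 1: "Cohort 1 subjects will all receive OMS721 4 mg/kg intravenously (IV) once weekly for 12 weeks"; the OMS721 arm of Cohort 2 has the same dose. For Cohort 3: "Subjects in Cohort 3 will receive either OMS721 370 mg IV or 5% dextrose in water (D5W) vehicle". Rollover subjects from Cohorts 1 and 2 move to open-label 370 mg weekly for what is left of their treatment period.

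Protocol section 13.2.10.1 asks for drug administration and treatment duration by disease, cohort and overall, and names no unit. Protocol section 9.2 says of site accountability records: "The documentation should include which drug product was used"; the text that follows is redacted.

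**The concern.** A volume measures dose only at a fixed concentration. With two concentrations in use, a mean or total in mL mixes two scales, and nothing in SAP section 13.3 or protocol section 13.2.10.1 converts it to mg. The primary objective is safety and tolerability, and the exposure table gives the context in which adverse events are read. A reader comparing weight-dosed Cohorts 1 and 2 with fixed-dose Cohort 3, or looking at an overall figure, could draw the wrong conclusion about who received more drug.

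There is a second gap. Cohort 3 is the largest planned cohort (18 of about 44 subjects), and section 13.3 gives it no intended-volume formula. Its intended volume and dose intensity are therefore undefined there. The 4 mg/kg formula also does not describe the 370 mg open-label doses of rollover subjects, and a vehicle subject in Cohort 2 has no drug concentration to divide by.

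**Working it through.** The plan states no exposure total or dose intensity, so there is no figure to reproduce.

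**Inputs.** From SAP section 13.3: concentrations of 100 and 185 mg/mL, and the definitions of intended volume and dose intensity. From SAP section 4: 4 mg/kg weekly for 12 weeks, and 370 mg. Body weights, dose counts below 12 and all assignments of product to subjects are my assumptions, for illustration.

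**1. Same dose, two volumes.** Volume = mg / concentration.
- 370 mg: 370/100 = 3.7 mL; 370/185 = 2.0 mL.
- Twelve doses: 44.4 mL against 24.0 mL.
- Ratio for any dose: 185/100 = 1.85, so 85% more volume at 100 mg/mL.

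**2. Order of subjects (both 70 kg, 4 mg/kg = 280 mg per dose).**
- 7 doses at 100 mg/mL: 1,960 mg, 19.6 mL.
- 12 doses at 185 mg/mL: 3,360 mg, 3,360/185 = 18.16 mL.

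The subject with fewer doses at the same weight shows the larger volume. The break-even is 12/1.85 = 6.49 doses.

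**3. Order of cohorts (70 kg, one product per cohort).**
- 280 mg at 100 mg/mL: 2.80 mL.
- 370 mg at 185 mg/mL: 2.00 mL.
- In mg the second dose is 370/280 = 1.32 times the first, so 32% higher. In mL it is 2.00/2.80 = 0.71 times the first, so 29% lower.

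Dose counts do not correct this, because equal counts are not equal mg across a weight-based and a fixed regimen.

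**4. Relative dose intensity, read as calculated per subject.** With one concentration c throughout, (sum of mg received / c) / (sum of mg intended / c) is the mg ratio. Nine of 12 equal doses give 75% either way.

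With both concentrations, suppose 6 doses of 370 mg are planned at each and 3 are missed:
- Intended volume: 6 × 3.7 + 6 × 2.0 = 34.2 mL.
- Three missed at 100 mg/mL: (34.2 − 11.1)/34.2 = 67.5%.
- Three missed at 185 mg/mL: (34.2 − 6.0)/34.2 = 82.5%.
- In mg: 9/12 = 75%.

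Over splits of 12 equal-mg doses between the products, the largest discrepancy is about 15 percentage points. For example, with 5 planned at 100 mg/mL and all given, and 7 planned at 185 mg/mL and all missed, the volume ratio is 5 × 1.85/(5 × 1.85 + 7) = 9.25/16.25 = 56.9%, against 5/12 = 41.7% in mg.

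**5. Rollover doses.** If the 4 mg/kg formula were applied to a 370 mg dose, intended and given would agree only at 370/4 = 92.5 kg. At 70 kg a full dose would score 370/280 = 132%.

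**The case against.** The case for leaving the table alone has real content.

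- **Dose intensity.** A reader might infer that the 85% gap carries into relative dose intensity. It does not. The intended volume is already divided by concentration, so concentration cancels for any subject on one product. Distortion needs a within-subject switch and an uneven shortfall, and the documents report no such switch. This objection stands.
- **Safety rates.** A reader might also infer that the primary safety results are computed on the wrong denominator. SAP sections 13.1 and 13.2 plan subject incidence, so the denominator is subjects, and no exposure-adjusted rate is planned. This stands too: exposure is context for those tables, not an input to them.
- **Other information.** The number of doses is summarised and dosing is listed. For OMS721 subjects in Cohort 3, number of doses times 370 mg gives the nominal mg, apart from partial infusions. It is therefore too strong to say that the amount of drug cannot be recovered. It can be, but by hand, and the planned summary does not show it.
- **Assignment of product.** The visible text does not say who received which concentration, and the packaging and dose-preparation sections are redacted. If each disease, cohort and treatment cell used one product, totals within a cell are sound. That limits the problem but does not remove it, because comparisons between cells and the overall summary required by the protocol would still mix scales if both products were given.
- **Body weight.** Under 4 mg/kg, a heavier subject has more mg at the same mg/kg, so mg alone would replace a concentration artefact with a weight artefact. This is fair for Cohorts 1 and 2, and is why mg/kg belongs in the fix.
- **Scale.** This is a descriptive table in a study of about 44 subjects with no planned tests, and the table shells are in a separate document that I have not seen.

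**Conclusion.** The specification is deficient in two respects. First, total exposure is summarised in mL although two concentrations are used. The same mg dose differs by 85% in volume, so totals pooled over or compared between products do not measure drug exposure and can misorder subjects or cohorts. Second, section 13.3 has no intended-volume formula for Cohort 3 and none that fits rollover subjects' open-label doses.

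The 85% follows exactly from the two stated concentrations. Its effect on the reported tables is unknown, because the assignment of products is not public. Relative dose intensity is affected only in subjects who receive both products with an uneven shortfall: 67.5% or 82.5% against 75% under the assumed 6+6 split with three missed doses. The documents do not support a claim that dose intensity is generally wrong, that adverse event incidences are affected, or that both products were in fact used for the 370 mg dose. The point is minor in consequence but worth correcting.

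**What to change.** Amend SAP section 13.3 and the matching table as follows.

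- For OMS721, summarise total mg received (volume given times the concentration of the product used), total mg intended, and relative dose intensity calculated from those mg totals.
- Take the intended dose from each cohort's regimen as documented: the weight-based rule with the SAP's own 100 kg cap for Cohorts 1 and 2, and the fixed dose for Cohort 3 and for open-label doses, including those of rollover subjects.
- Add mg/kg for Cohorts 1 and 2.
- For vehicle, report number of doses and volume only.

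The cost is a small change to SAP wording and one table. No new data are needed, because the formula already requires the concentration at each dose. The conversion assumes that the recorded dose volume is the volume of drug product, as that formula implies.
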